Version 1.0 del 16.12.2022

TITLE: CANCER MULTI-OMICS AVATARS FOR INTEGRATED PRECISION MEDICINE

SHORT TITLE: LANTERN

PROMOTER: Fondazione Policlinico Universitario A. Gemelli, U.O.C. di Thoracic Surgery– I.R.C.C.S.

PRINCIPAL INVESTIGATOR: [name], U.O.C. di Thoracic Surgery – I.R.C.C.S. Fondazione Policlinico Universitario A. Gemelli

ABSTRACT

Lung cancer is one of the most commonly diagnosed forms of cancer worldwide, accounting for approximately 12.2% of total cancer diagnoses. Despite the recent advances in treatment, prognosis still remains poor with a high mortality rate.

The current therapeutic approaches have reached a significantly high level of complexity, due to the recent identification of mutations and other cancer heterogeneity drivers (i.e., actionable mutations or PD-L1 expression for immunotherapy indication), thereby complicating the process of decision-making by clinicians.

The integration of "omics" datasets in different domains (i.e., genomics, proteomics) may further support clinicians in identifying innovative variables to support a new kind of comprehensive cancer care, towards personalized medicine.

In the last decade, significant improvements have been observed in the development of omics technologies, resulting in an overwhelming number of variables to be considered while making decisions that can be hardly handled by a human operator. Interestingly, with the advent of advanced Artificial intelligence (AI) techniques, more information can be obtained via "Internet of Things" technologies and various omics datasets which could be used efficaciously in creating predictive models.

These models can be used can be used either individually or merged in a multi-omics patient avatars to assist in the clinical decision-making process and introduce new paradigms of care and research, evaluating unexpected links among variables that were previously unexplored.

Therefore, the primary aim of the LANTERN project is to develop accurate predictive models for lung cancer patients, using various omics-based variables and integrating well-established clinical factors with "big data" and advanced imaging features. With this, individual patient avatars can be created which will serve as powerful tools in guiding clinicians and researchers in making more accurate decisions.

AUTHORS

Principal Investigators

Our consortium aims at fulfilling the objective of this year's call through the intersectional, multinational and interdisciplinary collaboration between University and clinical research teams and private organisations towards the implementation of personalised medicine, by combining clinical research with bio-informatics as well as ELSA research or implementation research. FPG components in Rome (https://gstep.policlinicogemelli.it), the coordinating site, has a sound background in translational research of advanced quantitative imaging analysis and AI based applications for personalized medicine and has been involved in several international trials on lung cancer. In a retrospective study, FPG researchers explored technical issues in personalized medicine through the prediction of NSCLC survival by quantitative image analysis, demonstrating the usefulness of density correction of volumetric CT data (Farchione et al., 2020). Recently, this research team also participated in a study involving a distributed learning performed on over 20,000 lung cancer patients by providing a privacy-by-design infrastructure (Personal Health Train), connecting FAIR (Findable, Accessible, Interoperable, Reusable) data sources from 5 different countries which enhanced distributed data analysis and ML (Deist et al., 2020). OncoRay, a national Centre for Radiation Research in Oncology, located in Dresden (TUD) (https://www.oncoray.de/center), is focused on applying ML/AI approaches to enable personalized radiation oncology based on big data, i.e. clinical imaging data (radiomics). In previous studies, their research team carried out a comparative study of machine learning methods for time-to-event survival data for radiomics risk modelling. From this study, they were able to identify a subset of algorithms which should be considered in future radiomics studies to develop stable and clinically relevant predictive models for time-to-event endpoints (Leger et al., 2017). HSCSP in Barcelona has a strong lung oncology research group, participating in numerous clinical trials in chemo-radiotherapy in lung cancer (Provencio et al., 2021), treating around 400 patients/year. In a recent retrospective study, HSCSP research team explored the effects of non-adherence to external beam radiation therapy on 1-year survival in cancer patients receiving treatment with a curative in Catalonia, Spain (Borras et al., 2020). DEB, is a renowned institution of higher education in Hungary, contributing immensely to the progress of clinical research with expertise in public health and play a major role in Ethico-legal aspects of personalised medicine research. In a Previous research project, FPG and DEB partnered with the PRECeDI consortium (http://www.precedi.eu/site), releasing a set of five recommendations for policy-makers, scientists and industry, including ethico-legal and policy recommendations, to foster the integration of PM approaches in the field of chronic disease prevention (Boccia et al., 2019). KU is a well recognized institute with over 150 research centres, forums, and laboratories that conduct high quality scientific research projects with expertise in Thoracic Surgery, Pathology, Bioinformatics and Network Modelling and Engineered Cancer & Organ Models. In Previous studies, KU researchers were involved in the development of a three-dimensional hydrogel model that can mimic the native glycosaminoglycans in tissues ([name] et al., 2016; [name] et al., 2017; Öztürket al., 2020). AdPEE is a patient organisation that ensures the active involvement of patients and caregivers in clinical research for constant and productive dialogue with decision-making bodies. (https://accademiadeipazienti.org/accademia-paziente-esperto-adpee/).

SUMMARY OF PROJECT RATIONALE AND WORKPLAN

The LANTERN project was developed, based on 4 Work Packages (WP):

i. WP1: Patient enrollment and omics data collection [Months 1-30].

Objective: To gather information from all the clinical and omics based data sources acknowledged as clinically significant or decision support variables for lung cancer comprehensive diagnosis and therapy workflow definition. A structured terminological system will be developed for prospective data collection through specific Case Report Forms (CRFs).

Methodology: The five main omics data tiers to be collected in this project, reflecting all the involved omics domains in the lung-cancer decision making pathway are: A. Demographic and physiological data; B. Medical history, clinic-functional, laboratory data and treatment information; C. Histo-pathological, immunological and genetic data; D. Radiomics and quantitative imaging data; E. Internet of Things derived data.

ii. WP2: Omics data archiving and inter-actionability [Months 2-30].

Objective: To ensure easy and effective omics data inter-actionability and to allow their complete integration into archiving systems and ad hoc digital platforms for data recording.

Methodology: A standard unit of measurement will be used in order to record the single variables. Possible discrepancies originated from the use of different scales, will be solved through shared equivalence decision. All the laboratory data used in WP1 will undergo cross quality assurance (QA) procedures among the centres and all the images used in WP1 will have to adhere to the standard "dicom" format (.dcm).

iii. WP3: Omics data modelling and avatar creation [Months 12-32].

Objective: To set up dedicated multi-omics data models and create lung cancer Digital Human Avatars (DHA).

Methodology: An exploratory analysis across all collected datasets to enable the start of the biomarker identification process; followed by the set-up of multiple distinct modular multivariate models, trained though advanced ML and AI techniques; and validated through internal and external validation to test their robustness, transferability and generalizability.

iv. WP4: DHA towards implementation in healthcare [Months 1-36].

Objective: To enable feedback data loops for preventive healthcare strategies and Quality of life (QoI) and to ensure that all the potential stakeholders are involved in the process of development of DHA for a fast uptake into daily practice.

Methodology: All necessary factors (clinical, epidemiological, technical, economic, organizational, social, legal and ethical implications) will be considered for the proper implementation of the DHA in healthcare. To

Protocol LANTERN_v1.0 del 16.12.2022

this aim, a robust and rigorous scientific methodology will be applied by combining quantitative approaches (collection of scientific evidence and systematic literature reviews/meta-analysis; consultation of institutional flows and databases/hospital discharge forms/national price lists and data analyses; mathematical models; cost-utility/budget impact analyses) and qualitative research techniques (Consensus conference, Focus group, Delphi, Expert opinion).

The LANTERN project is configured as highly innovative, since for the first time in the field of lung cancer research, we intend to develop a predictive platform powered by the integrated reading of data from the main omics sciences. The project has the ambition to combine data from radiomics with clinical and biological data, derived from biological omics (through the analysis of the patient's biological samples) on a digital platform. This project though seems ambiguous, has a well-thought out plan and is highly feasible through the cooperative work efforts and experience of each consortium partner in their respective fields. With the commitment of each partnering centre in undertaking their respective delegated tasks as described in the project work plans and tasks, We believe the LANTERN project will be completed within a timeframe of 3 years which aligns with the expected time taken for the project completion as stated in the call document.

Personalised medicine represents an evolution from traditional "one size fits all" strategies, extending the concept of stratifying cancer treatments on well-known clinical and pathological characteristics to a more individual, patients specific, truly personalized level. However, the current approach typically relies on molecular and cellular data-sets (i.e. mutations) that are very limited and relative only to subsets of the complex web of cellular data that determine treatment outcomes. Due to various histological, genetic, immunological and imaging characteristics that define its highly variable oncological outcomes, lung cancer represents an ideal case to run AI based multidimensional personalized medicine studies, thereby fitting into the purpose of this project.

AIMS

Main objectives

The aim of LANTERN project is to develop accurate predictive models for lung cancer patients, using different omics-based variables, integrating well established clinical factors with big data and advanced imaging

features. This technological solution will be able to capture patients' conditions at multiple levels, supporting an effective disease prevention and further reducing the healthcare costs through personalized treatments.

More specifically, we will develop Digital Human Avatars (DHA) defined as computerized representations of individual patients and their characteristics, with a specific focus on advanced biological functions, as well as relevant pathological variables, which will be modelled, sourced and parametrized in a cutting-edge experimental "big data" setting.

Secondary objectives

Our main goals are:

i. To gather information from all the clinical and omics-based data sources acknowledged as clinically significant

ii. To ensure an easy and effective omics data inter-actionability and to allow their complete integration into archiving systems

- iii. To set up dedicated multi-omics data models and create a comprehensive lung cancer DHA
- iv. To enable feedback data loops for preventive healthcare strategies and quality of life (QoL) management
- v. To ensure that all the potential stakeholders are involved in the DHA development process.

METHODOLOGY

This is a prospective observational study

WP1: Omics data collection

The five main omics data tiers that will be identified as the ontology of this project, reflecting all the involved omics domains in the lung-cancer decision making pathway are: A. Demographic and physiological data; B. Medical history, clinic-functional, laboratory data and treatment information; C. Histo-pathological, immunological and genetic data; D. Radiomics and quantitative imaging data; E. Internet of Things derived data.

A structured terminological system for prospective collection of anonymized data will be developed, creating a dedicated database for all omics domains considered. The data will be stored in a dedicated server and categorized according to the data reported in the WP1. Researchers will provide a structured terminological system for prospective collection of anonymized data in which all information will be recorded through specific Case Report Forms (CRFs), ensuring uniformity and consistency for all variables collected. Tumour

samples from all enrolling centres will be stored at the coordinating centre in a dedicated laboratory (**FPG**). In-house samples will be collected immediately after biopsy or surgery, while samples from other RUs will be delivered using an appropriate courier service following standard international rules and laws. A comprehensive molecular characterization and genomic profiling of tumour samples will be performed using the Illumina TruSightTM, which will allow the conversion of DNA and RNA extracted from formalin-fixed paraffin-embedded tissue samples into libraries enriched for cancer-related molecular targets. In our methodological approach, we will assess both DNA and RNA levels using a single high-throughput assay that evaluates a wide range of state-of-the-art clinical biomarkers. Specifically, we will analyze with high fidelity multiple somatic genomic alterations such as low-frequency somatic variants (single nucleotide variants, insertions and deletions, and splice variants) and copy number alterations (CNAs) in identified genes linked to cancer susceptibility and treatment.

WP2: omics data archiving and inter-actionability

The aim of this WP is to allow complete data integration into both existing and new archiving systems (Task 2.1: Data archiving QA), and to ensure an easy and effective omics data inter-actionability (Task 2.2: Interactionability QA). All the considered variables will be recorded according to a shared common ontology based on the variable-specific domains, in order to enhance their direct actionability. A standard unit of measurement will be used in order to record the single variables. Possible discrepancies originated from the use of different scales, will be solved through shared equivalence decision. All the laboratory data used in WP1 (Data A, B, C) will undergo cross quality assurance (QA) procedures among the involved centres prior to data upload in the shared platform. Patient data from **KU**, **DEB** and **HSCSP** will be transferred to **FPG** and **TUD** for the radiomic analysis. The shared general ontology will represent a structured terminological system for data archiving and analysis, granting uniformity and coherence for all the collected variables.

Proposed radiomic analysis will be as follows: first, gross tumour volume (GTV) delineation will be performed retrospectively by experienced lung malignancy Radiotherapy Oncologists on each patient's images (CT images in DICOM (.dcm) format). DICOM files containing not only the CT images but also the RT structure file will be exported and processed using MODDICOM, an R package developed to optimize automatic loading of DICOM images and radiomic analysis. Radiomic features will then be extracted automatically. The extracted radiomic features belong to different families: Intensity-based, morphological, textural and fractal. All analyzed image features will be based on the standardization criteria of the IBSI initiative.

WP3: omics data modelling, avatar creation and knowledge transfer

Developing accurate predictive models and creating Digital Human Avatars (DHA) - Omics features identification and selection: In the first step, an exploratory analysis across all collected datasets (An estimate of \approx 240 NSCLC patients) will enable the start of the biomarker identification process and restrict the cast amount of information towards a more selected pool of potential biomarkers. This first phase will employ robust data analysis techniques in order to identify relevant variables (T3.1.) in a univariate setting, taking individual statistical distributions, feature-relevant correlations and general descriptive statistics into account.

Patient selection

INCLUSION CRITERIA:

- Patients with (suspected) NSCLC
- Age >18 yrs
- ECOG 0-3
- Written Informed Consent

EXCLUSION CRITERIA:

- ECOG 4
- Psychosocial, or emotional conditions controindicating participation to the study

STATISTICAL ANALYSIS METHODOLOGY

An estimate of 600 Patients (both male and female) with \geq 18 years of age with pathologically proven diagnosis of non-small cell lung cancer (NSCLC) will be enrolled. Sample size was calculated on the basis of G-powerR program for "a priori" analysis, considering α =5% and power of 90%.

The Wilcoxon Mann-Whitney (WMW) test will be used to investigate the ability of these features to predict clinical outcomes on univariate analysis, and the feature showing the lowest p-value will be considered as the most predictive parameter. Receiver Operating Feature curve analysis (ROC) will also be performed on the most significant feature obtained at WMW analysis, calculating the area under the curve (AUC) with the corresponding 95% confidence interval (CI) according to the Clopper-Pearson method. Model processing will be performed through advanced ML and AI techniques first on a dedicated training dataset to fit the model parameters. The obtained hyperparameters will be tuned on a dedicated validation dataset and finally a test dataset will be employed as a dataset independent of the training dataset but following the same probability distribution.

Predictive model development

The objective of the second phase is creating multiple distinct but modular multivariate models, trained through advanced ML and AI techniques and segmented into specific modular areas of interest (T.3.2).

Different supervised models will be developed including logistic regression, decision tree, support vector machine, random forest, XGBoost classifier, and artificial neural networks. The k-fold cross-validation will be used for hyperparameters tuning. The final step in the proposed methodology is the statistical significance comparison of the performance of the ML models. This will be done evaluating predictive performances in terms of different metrics: the first evaluation will be based on accuracy (number of subjects correctly classified on the total number of patients) while the other will be on precision (true positive on total test positive), recall (sensitivity), F1 score (2*precision*recall/(precision+recall)) and AUC-ROC.

We estimate about 300 NSCLC cases with complete data to start developing the models. Specific care will be taken to always ensure both user friendliness and model explainability as primary pillars of the model development strategies. Easily interpretable values such as SHAP (SHapley Additive exPlanations) values will be attached to each model in order to avoid any black-box approaches that might render model outputs, difficult to explain to the patients during their interactions with the clinicians.

Predictive model validation

Both the developed model and the comprehensive DHA will be validated in order to test their robustness, transferability and generalizability. Two consecutive validation strategies will be employed respectively: the internal and external validation techniques. We estimate a total number of \approx 420 NSCLC cases to start the validation process. This process will include both internal and external validation. The internal validation step will be focused mainly on techniques such as K-fold cross validation. This will allow to achieve a Transparent Reporting of a multivariable prediction model for Individual Prognosis Or Diagnosis (TRIPOD) level 2b. At this TRIPOD level, data are non-randomly split (e.g., by location or time) into 2 groups: one to develop the prediction model and the remaining dataset to evaluate its predictive performance. In the case of suboptimal performances, all the failing models will be reverted back to the previous stage and the models will be retrained with new specifications in order to increase their robustness. At this point, the models can be validated using external datasets, reaching TRIPOD 3 and 4 levels (External validation). Finally, when the models reach a TRIPOD 4 level, data transferability and full actionability will be granted, allowing the successful and safe application of the model in the clinical Routine (T3.3).

ETHICAL CONSIDERATIONS

Considering the technicality and complexity of the LATERN Project, consortium partners are well aware of the various ethical and legal questions relating to the project. The main ethical issues related to this project include:

the respect for persons and for human dignity; fair distribution of benefits and burden; the rights and interests of the participants; the need to ensure participants' informed consent; processing of personal data; concerns involving the development, deployment and/or use of artificial intelligence (AI)-based systems or techniques.

Protocol LANTERN_v1.0 del 16.12.2022

Therefore, LATERN partners will identify and implement a comprehensive set of ethical and legal requirements in accordance with Declaration of Helsinki principles to ensure compliance for all activities of the project. Appropriate ethical monitoring systems will also be set up.

To this effect, LATERN will implement the following activities:

Participation in this study must be entirely voluntary and fully informed consents of the participants must be obtained via project-specific **Informed consent forms** which must be documented before their participation in this project.

• Obtaining ethical approvals by the relevant competent national/local ethics authorities in relation with project protocol (i.e., For using or storing human cells or tissues for genetic testing), according to each country's specific ethics requirements and legislation

• Personal data obtained in this study must be processed in an pseudomised format and Information about the data processing operations and the contact details of the data protection officer must be provided to the participants in accordance to applicable EU regulations (art 13/art 14 GDPR).

• The development and deployment of AI-models will be based on specific ethical- approaches which must guarantee privacy and data protection throughout the system's lifecycle. The adopted approach will be built upon key prerequisites that align with "Assessment List for Trustworthy Artificial Intelligence" (ALTAI) in order to establish procedures to detect, assess the level and address potential risks for the production of ethically sound AI models.

• Monitoring compliance with set of ethical and legal requirements defined at EU and national level.

BIBLIOGRAPHY

• Molina JR, et al. AA. Non–small cell lung cancer: epidemiology, risk factors, treatment, and survivorship. Mayo Clin Proc. 2008;83:584-594

• Pastorino U, et al. Prolonged lung cancer screening reduced 10-year mortality in the MILD trial: new confirmation of lung cancer screening efficacy. Ann Oncol. 2019 Oct 1;30(10):1672. doi: 10.1093/annonc/mdz169. Erratum for: Ann Oncol. 2019 Jul 1;30(7):1162-1169. PMID: 31168572 [3] Holzinger A, et al. Knowledge discovery and data mining in biomedical informatics: the future is in integrative,

interactive machine learning solutions. Interactive knowledge discovery and data mining in biomedical informatics: state-of-the-art and future challenges. Lecture notes in computer science LNCS 8401. In: Holzinger A and Jurisica I, editors. Springer; 2014. p. 1–18.

• Salehi-Rad R, et al. The Biology of Lung Cancer: Development of More Effective Methods for Prevention, Diagnosis, and Treatment. Clin Chest Med. 2020 Mar;41(1):25-38. doi:

• 10.1016/j.ccm.2019.10.003. PMID: 32008627.

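### The univariate feature screen at about 240 patients is neither confined to training patients nor repeated within cross-validation folds, so internal validation can be optimistic

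*Combined protocol and SAP*

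**What the plan says.** All references are to the combined protocol and SAP.

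- **WP3: omics data modelling, avatar creation and knowledge transfer.** The first step is "an exploratory analysis across all collected datasets", with an estimated 240 NSCLC patients. Its purpose is that it "will enable the start of the biomarker identification process and restrict the cast amount of information towards a more selected pool of potential biomarkers". The techniques are applied "in order to identify relevant variables (T3.1.) in a univariate setting".
- **Summary of project rationale and workplan.** The order is the same: the exploratory analysis comes first, "followed by the set-up of multiple distinct modular multivariate models", and validation is last. Enrolment runs over months 1–30 and modelling over months 12–32, so patients are still being enrolled when modelling begins.
- **Statistical analysis methodology.** The Wilcoxon Mann-Whitney (WMW) test relates features to clinical outcomes one at a time, and "the feature showing the lowest p-value will be considered as the most predictive parameter". Training data are mentioned after this, for model processing: "first on a dedicated training dataset to fit the model parameters". The later test dataset is to be independent of the training dataset; its relation to the screen is not stated.
- **Predictive model development.** About 300 complete cases start model development. K-fold cross-validation is assigned to hyperparameter tuning.
- **Predictive model validation.** About 420 cases start validation. Internal validation is mainly k-fold cross-validation. A non-random split, for example by location or time, is described for TRIPOD level 2b. Models with suboptimal performance return to the previous stage.

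**The concern.** Cross-validation gives an honest estimate only if every step that looked at the outcome is repeated without the patients being tested. If features are chosen once, using outcomes of patients who later sit in test folds, those folds have already helped pick the features that happen to fit them. The resulting AUC is too high even when the model fitting itself is kept clean.

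The project's main aim is accurate prediction, and internal performance decides which models are sent back. An inflated figure lets a weak model through. External validation could expose this, but only later.

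**Working it through.** **1. Does any section protect the test patients?** The four places where protection could appear are the WP3 step, the WMW paragraph, the cross-validation sentence and the validation section. None limits the screen to training patients, excludes hold-out patients from it, or repeats it in folds.

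**2. How many tested patients were already screened?** This assumes the patient counts are cumulative. Even accrual of 600 over 30 months fits that reading: 600 × 12/30 = 240 at month 12, when WP3 starts; 600 × 15/30 = 300; 600 × 21/30 = 420. In k-fold cross-validation of n patients, or a random hold-out from them, the expected screened share of the tested patients is 240/n:

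- n = 300: 240/300 = 80%
- n = 420: 240/420 = 57%
- n = 600: 240/600 = 40%

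A hold-out centre accruing at the same pace as the others has the same share.

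**3. How large is the optimism?** The documents give no event rate, feature count or number kept, so these are assumptions: 30% events; 100 or 500 normal features, independent or in blocks of 10 with correlation 0.7; 10 features kept by WMW on the first 240 patients; a logistic model; 5-fold cross-validation. Weak real signal means five features, each with a single-feature AUC of 0.58. In the correlated case their block-mates carry 0.7 of that signal. Optimism is the reported AUC minus the AUC in new patients.

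| Patients cross-validated | Pure noise (true AUC 0.50), 240-patient pool | Pure noise, screen inside folds | Weak real signal, 240-patient pool: optimism |
|---|---|---|---|
| 300 | 0.57–0.71 | about 0.50 | 0.04–0.17 |
| 420 | 0.54–0.64 | about 0.50 | 0.03–0.12 |
| 600 | 0.53–0.60 | about 0.50 | 0.02–0.07 |

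A rerun for this write-up agreed with these ranges to within 0.01. The low ends come from 100 correlated features, the high ends from 500 independent ones. More features make it worse: with 2000 noise features (30% or 50% events, 10 or 20 kept, ridge logistic model), cross-validating 300 patients gave 0.72–0.79.

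**4. Components at 600 patients, random 30% test set, real signal.**

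- 500 independent features: 0.638 − 0.566 = 0.072
- 100 independent features: 0.645 − 0.606 = 0.039
- 500 correlated features: 0.61 − 0.57 = 0.04
- 100 correlated features: 0.62 − 0.60 = 0.02

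**5. When does the problem vanish?** With independent features and the same 240-patient pool, but a test set enrolled after the screen, reported against new-patient AUC was 0.555 against 0.560 (500 features) and 0.603 against 0.601 (100 features). Screening in training patients only gave 0.582 against 0.584 and 0.611 against 0.614. Neither shows optimism.

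**The case against.** The strongest reply is that this is silence, not a stated leak.

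- The document also uses the word datasets for omics domains, so the WP3 phrase may mean all data tiers, not all patients.
- No section dates the split. That the screen precedes it is inferred from the order of the text.
- The WP3 paragraph mentions distributions, correlations and descriptive statistics, not an outcome. The WMW test sits in another section, and its stated use is to name the single best feature for ROC analysis.
- The step is said only to start biomarker identification, and failing models can be respecified, so nothing fixes the pool at 240.
- The TRIPOD 2b description gives one group to development, which ordinarily includes feature selection. Clinical use waits for TRIPOD level 4, after external validation.

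Most of this stands, and it rules out stronger readings. A reader might infer that the plan screens hold-out patients, that the pool is permanently fixed at 240, or that all 600 patients are screened before modelling. The documents state none of these, and the last conflicts with the figure of about 240.

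The k-fold problem remains. Cross-validation tests every development patient in turn, so even a screen confined to the development group biases the result unless it is repeated in each fold. Reading datasets as omics domains does not change this. The outcome-based WMW is also the only univariate test named, so it is the natural tool for a univariate search for relevant variables.

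**Conclusion.** The point holds as a conditional one. If the narrowing uses the outcome and the described order is followed, k-fold performance will be optimistic, as will any random or by-location hold-out that contains screened patients. The gate that returns only suboptimal models is weakened accordingly. A screen that ignores the outcome would not create this problem, and later-enrolled or external test patients are unaffected, so the point does not extend to external validation.

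Under the stated assumptions the optimism is largest where modelling starts and shrinks as unscreened patients are added. The figures show direction and plausible size; they are not estimates for this study. The plan should be changed, because the correction is cheap and internal performance decides which models go forward.

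**What to change.** Add to the WP3 methodology, the statistical analysis section and the validation section wording such as:

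*Outcome-based feature screening uses development (training) patients only and is repeated within each cross-validation fold. The hold-out centre(s) or enrolment date is fixed before any outcome-based screen. The screen at about 240 patients is provisional and is rerun on the full development set.*

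**Cost.** One extra analysis run and no extra patients. Reported internal performance will be lower: in the independent-feature examples at 600 patients it falls from 0.638 to 0.582 (500 features) and from 0.645 to 0.611 (100 features). AUC in new patients does not suffer relative to the 240-patient pool (0.584 against 0.566, and 0.614 against 0.606).

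The final screen uses fewer patients than the whole cohort. The single-feature AUC detectable with 90% power (two-sided 5%, 30% events assumed) is Φ(d/√2), with d = 3.2415 × √[(1/n1 + 1/n0) × π/3]. If 30% of 600 are held out, 420 remain (n1 = 126, n0 = 294): d = 0.353, AUC 0.599. All 600 would give 0.583. The provisional 240 (n1 = 72, n0 = 168) gives d = 0.467, AUC 0.629, so the rerun is still more sensitive than the screen at 240.
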